We will stratify analyses based on baseline disease severity (estimated 5-year relative survival risk) and disease status (progression, lymph node involvement, other sites of metastases).

All subjects will be accrued from the Mass General Brigham healthcare system, which includes two academic medical centers, a specialty head and neck hospital, and multiple community hospitals and numerous community clinics.

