## 5 STUDY POPULATION

### 5.1 INCLUSION CRITERIA

In order to be included in this study, an individual must meet all of the following criteria:

1. Age  $\geq 18$
2. Thyroid nodule on PET-CT performed 1/1/2015 to 12/31/2021
3. At least one clinical note in the EHR from the 36-month window prior to the PET

Note, there are no restrictions on the indication for the index PET-CT.

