ckd	Mortality Risk Adjustor: Chronic Kidney Disease: ICD-10 N18; ICD-9 585; recorded prior to date of imaging examination
cancer	Mortality Risk Adjustor: Cancer: ICD-10 C00-C96; ICD-9 140-209; recorded prior to date of imaging examination
obesity_icd	Mortality Risk Adjustor: Diagnosis of obesity (ICD-10 E66, ICD-9 278.00 or 278.01) at time of imaging examination
bmi	Mortality Risk Adjustor: Body mass index at time of imaging examination
hncancer_binary	Mortality Risk Adjustor: Head/Neck Cancer: ICD-10 C00-C14; ICD-9 140-149; recorded prior to date of imaging examination
radiation_binary	Mortality Risk Adjustor: Radiation Therapy: CPT 77401-77416, G6003-G6014, 77385-77386, G6015-G6016
priorneckradiation	Mortality Risk Adjustor: Prior head/neck cancer radiation therapy (ICD-10 C00-C14 or ICD-9 140-149 and CPT 77401-77416, G6003-G6014, 77385-77386, or G6015-G6016 both recorded prior to date of imaging examination, then priorneck radiation =1; otherwise, 0)
Fiveyr_atPET	Mortality Risk Adjustor: 5 year survival probability associated with cancer dx received before PET exam (if multiple cancers before PET, lowest survival probability)
NeckNodes	Potential Confounder: 1= PET-CT report indicates that there are neck or supraclavicular lymph node metastases
AxillaryNodes	Potential Confounder: 1= PET-CT report indicates that there are axillary lymph node metastases
MediastinalNodes	Potential Confounder: 1= PET-CT report indicates that there are mediastinal (including paratracheal, paraesophageal, prevascular, subcarinal, perihilar, or hilar) lymph node metastases
AbdominalNodes	Potential Confounder: 1= PET-CT report indicates that there are abdominal (including peri-portal, celiac, mesenteric, retroperitoneal, iliac) lymph node metastases
InguinalNodes	Potential Confounder: 1= PET-CT report indicates that there are inguinal lymph node metastases

Brain	Potential Confounder: 1= PET-CT report indicate that there is likely primary malignancy or metastases in the lungs
Face	Potential Confounder: 1= PET-CT report indicate that there is likely primary malignancy or metastases in the face (e.g. pharynx, salivary glands, etc)
Lung	Potential Confounder: 1= PET-CT report indicate that there is likely primary malignancy or metastases in the lungs
Pleura	Potential Confounder: 1= PET-CT report indicate that there is likely primary malignancy or metastases in the pleura

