Mediastinum	Potential Confounder: 1= PET-CT report indicate that there is likely primary malignancy or non-nodal metastases in the mediastinum
Liver	Potential Confounder: 1= PET-CT report indicate that there is likely primary malignancy or metastases in the liver
Spleen	Potential Confounder: 1= PET-CT report indicate that there is likely primary malignancy or metastases in the spleen
Kidney	Potential Confounder: 1= PET-CT report indicate that there is likely primary malignancy or metastases in the kidneys
Adrenal	Potential Confounder: 1= PET-CT report indicate that there is likely primary malignancy or metastases in the adrenal glands
Pancreas	Potential Confounder: 1= PET-CT report indicate that there is likely primary malignancy or metastases in the pancreas
GI	Potential Confounder: 1= PET-CT report indicate that there is likely primary malignancy or metastases in the GI tract
Pelvis	Potential Confounder: 1= PET-CT report indicate that there is likely primary malignancy or non-nodal metastases in the pelvis
Peritoneum	Potential Confounder: 1= PET-CT report indicate that there is likely primary malignancy or metastases in the peritoneum/omentum
Bone	Potential Confounder: 1= PET-CT report indicates that there is likely primary malignance or metastases in the bones
Muscle	Potential Confounder: 1= PET-CT report indicate that there is likely primary malignancy or metastases in the muscles

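### The five nodal PET-report flags count only metastases and no flag covers unlisted sites, so node-only lymphoma or isolated breast or skin disease is coded like a clean PET.

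*Combined protocol and SAP*

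**What the plan says.** Section 7 (Additional Patient Variables) lists 20 disease-status flags drawn from the PET-CT report: five nodal regions and 15 organs or regions.

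- **Nodal flags.** NeckNodes is 1 when the "PET-CT report indicates that there are neck or supraclavicular lymph node metastases". The axillary, mediastinal, abdominal and inguinal flags use the same criterion, metastases.
- **Organ flags.** These are wider. The spleen flag is set for "likely primary malignancy or metastases in the spleen", and the last flag reads "PET-CT report indicate that there is likely primary malignancy or metastases in the muscles". Mediastinum is set for "likely primary malignancy or non-nodal metastases in the mediastinum", and Pelvis is worded in the same way. Face covers "likely primary malignancy or metastases in the face (e.g. pharynx, salivary glands, etc".
- **Other cancer covariates.** The variable cancer is any cancer code recorded before the PET. Fiveyr_atPET is a survival probability attached to a cancer diagnosis made before the PET.
- **Use.** Section 4.1 adjusts for the variables labelled in Section 7 as demographic, potential confounder or mortality risk adjustor. Step 3 of the analysis in the Section 1.2 table puts baseline factors into the adherence model that supplies the weights. Sections 4.1 and 8.4.5 also stratify by disease status, which Section 4.1 describes as "disease status (progression, lymph node involvement, other sites of metastases".
- **Population.** Section 5.1 notes that "there are no restrictions on the indication for the index PET-CT".

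**The concern.** Disease activity at PET plausibly affects both 7-year mortality and the decision to work up an incidental thyroid nodule, so it is a confounder the weights need to capture. The 20 flags are the plan's only direct record of it. Lymphoma is a primary malignancy of lymph nodes, yet the nodal flags do not accept a primary. Disease limited to the breast or skin has no flag at all. Because any PET indication is eligible, such patients can enter the cohort.

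If they are coded as free of active disease, the step 3 weights cannot balance them between strategies. Section 8.4 plans no sensitivity analysis for unmeasured confounding that would reveal the problem. Strata built from these flags would also place node-only lymphoma among patients without nodal disease, although Section 4.1 speaks more broadly of involvement.

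**Working it through.** The plan gives no figure on this point to reproduce. The check is a reading of the definitions, followed by an illustration.

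**1. Count of flags.** Nodal: Neck, Axillary, Mediastinal, Abdominal, Inguinal = 5. Organ: Brain, Face, Lung, Pleura, Mediastinum, Liver, Spleen, Kidney, Adrenal, Pancreas, GI, Pelvis, Peritoneum, Bone, Muscle = 15. Total 5 + 15 = 20. (The opening of Section 7 speaks of 12 such variables, and the Brain flag is defined by the lungs. Both are separate drafting errors.)

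**2. Which active disease sets a flag, read literally.**

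| Active disease on PET | Nodal flag | Organ flag |
|---|---|---|
| Carcinoma metastatic to a listed node region | yes | depends on other sites |
| Lymphoma in spleen, bone, liver, lung or GI tract | no | yes |
| Lymphoma reported as a mediastinal or pelvic primary | no | yes (non-nodal limits only the metastases) |
| Lymphoma confined to lymph nodes, not reported as such a primary | no | no |
| Breast or skin disease with spread to a listed site | as applicable | as applicable |
| Isolated breast or skin disease | no | no |
| Isolated laryngeal disease | no | unclear (Face is open-ended) |

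**3. Do other covariates fill the gap?** For a given earlier diagnosis, cancer and Fiveyr_atPET take the same value in active disease and in remission. Section 4.1 names progression, but Section 7 lists no progression variable and no overall active-disease variable. PET type, care level, referring department and radiation therapy are at most partial proxies.

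**4. Illustration of size.** Every input here is assumed; none comes from the documents. Let u be the share of the cohort with uncoded active disease, a1 its probability of ultrasound, a0 the probability in everyone else, and d the excess 7-year mortality. Ultrasound is taken to have no true effect.

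- Uncoded share among scanned = u·a1 / [u·a1 + (1−u)·a0]
- Uncoded share among unscanned = u·(1−a1) / [u·(1−a1) + (1−u)·(1−a0)]
- Crude bias in the risk difference (no ultrasound minus ultrasound) = (unscanned share − scanned share) × d

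With d = 20 points:

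| u | a1 vs a0 | Scanned share | Unscanned share | Bias (points) |
|---|---|---|---|---|
| 5% | 10% vs 20% | 0.005/0.195 = 2.56% | 0.045/0.805 = 5.59% | +0.61 |
| 10% | 10% vs 20% | 0.010/0.190 = 5.26% | 0.090/0.810 = 11.11% | +1.17 |
| 5% | 30% vs 20% | 0.015/0.205 = 7.32% | 0.035/0.795 = 4.40% | −0.58 |
| 10% | 30% vs 20% | 0.030/0.210 = 14.29% | 0.070/0.790 = 8.86% | −1.08 |

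A positive bias raises the upper confidence limit and works against non-inferiority. A negative bias works towards it. For the under-scanned case, widening the inputs to uptake of 10% vs 20%, 10% vs 30% or 20% vs 30%, and d from 10 to 40 points, gives +0.23 to +1.85 points at u = 5% and +0.44 to +3.57 at u = 10%. These are crude figures at a single decision time; adjustment for correlated covariates would shrink them.

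**The case against.** The strongest objection is that these lines are short variable descriptions, not the instructions given to the language model, which are not in the document. Section 4.1 shows that the intended concept is involvement, so lymphomatous nodes may in practice be coded 1. That is possible, but the Section 7 definition is the pre-specified one and it differs from Section 4.1. The two should be reconciled.

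A reader might infer that active lymphoma in general is coded like remission. The documents do not support that: extranodal disease, or a mediastinal or pelvic primary, can set an organ flag. Likewise, breast, skin or laryngeal cancer that has spread to a listed site is flagged. A reader might also infer that the larynx is clearly left out. It may fall under the open-ended wording of Face, and whether the coded head and neck range in Section 7 misses it cannot be settled from the documents, so no change to those codes is proposed here.

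It is also fair to say that residual confounding is plausible but not shown. The documents give no ultrasound uptake by disease activity and no share of patients with these presentations, and several adjusted covariates are partial proxies. The more intuitive scenario, fewer ultrasounds in active disease, costs power and does not produce a false claim of non-inferiority. The opposite scenario, more neck imaging in neck disease, does carry that risk. Finally, Sections 4.1 and 8.4.5 do not say how strata are built from the flags, so misplacement there follows only if the nodal flags define nodal disease.

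**Conclusion.** The point holds in a limited form. As written, lymphoma confined to lymph nodes and active disease confined to an unlisted site are coded 0 on all 20 flags, exactly as a clean PET is, and no other covariate separates active from remitted disease. This can leave residual confounding in the step 3 weights and misclassify the disease-status strata.

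Its size cannot be derived from the documents. Under the assumed inputs shown, a 5% to 10% affected share and a 20-point mortality gap give a bias of roughly half a point to just over one point, in either direction, against the 5-point margin. That is not enough to say the primary conclusion would be wrong. It is enough to justify a cheap correction before analysis. The conclusion rests on a literal reading of Section 7 and on ultrasound use differing by disease activity.

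**What to change.** - In Section 7, define all five nodal flags as malignant lymph node involvement, either metastasis or lymphoma, to agree with Section 4.1.
- Add one flag for active malignancy at any other site, naming breast, skin and subcutaneous tissue, and non-nodal neck tissue. State whether larynx belongs here or under Face. All flags at zero then means that no active disease was reported.
- Re-run the report extraction, and use the revised flags in the step 3 weights and the Section 8.4.5 strata.
- If any size of bias is reported, label it as an illustration with assumed inputs and state its direction.

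The cost is one prompt revision, one re-run on reports the tool already reads, about one more covariate in the weight model, and a wording change to the protocol. No new patients or data source are needed.

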### 1.2 TARGET VS. EMULATED TRIAL TABLE

	Target Clinical Trial	Observational Emulation
Design	Non-inferiority randomized controlled trial	Retrospective non-inferiority cohort study
Aim	Assess whether all-cause mortality in patients with an incidental thyroid nodule on PET-CT who did	Same

	not have thyroid ultrasound within 3 months is no worse than 5% higher than those who did have ultrasound	
Inclusion	Thyroid nodule on PET-CT Age 18 or older Clinic note within 36-months before the PET-CT	Same, with PET-CT scans between 1/1/2015 to 12/31/2021
Exclusion	Prior PET reported thyroid nodule Thyroid ultrasound in prior 3 years Prior thyroid cancer diagnosis	Same
Treatment Strategies	(1) Thyroid ultrasound ordered to be performed within 3 months (2) No thyroid ultrasound ordered	(1) Thyroid ultrasound performed within 3 months (2) No thyroid ultrasound performed within 3 months
Treatment Assignment	Randomized to treatment strategy	Non-randomized to treatment strategy. Randomization emulated via cloning patients in both arms.
Treatment Implementation	3-month grace period	3-month grace period
Outcome	All-cause mortality	Same
Type of Outcome	Failure time	Same
Follow-up Start	PET-CT date, equivalent to treatment assignment	PET-CT date, not equivalent to treatment assignment
Follow-up End	Earliest of death, 7-years from follow-up start, or study end	Same
Censoring	Administrative censoring	Administrative censoring Artificial censoring of clones
Causal Contrast	Intention to treat and per protocol	Per protocol effect only
Non-Inferiority Margin	5%	Same
Statistical Analysis	Non-inferiority intention to treat analysis that consists of comparing probability of mortality between treatment groups at 7 years.	Non-inferiority analysis using clone-censor-weight strategy: 1. Each subject is cloned at study

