	
Kaplan-Meier to estimate probability of mortality in each arm
 
Construct a 95% confidence interval for the absolute difference between the two arms, <math>\Delta_{RD}</math>
 
Taking the type I error rate, alpha, to be 0.05, non-inferiority is concluded if the upper limit of a two-sided 90% = 100(1-2alpha)% confidence interval for <math>\Delta_{RD}</math> is less than the prespecified margin.
	
baseline; one clone assigned to each treatment strategy.
 
2. Person-time for each clones is censored when their observed treatment strategy is non-adherent. That is, clones assigned to undergo thyroid ultrasound within 3 months are censored at 3 months of follow-up if no ultrasound is performed. Similarly, clones assigned to not undergo an ultrasound within 3 months are censored at the time an ultrasound is performed.
 
3. A pooled logistic regression model is fit for the (conditional) probability of adherence, adjusting for a priori specified baseline factors that predict adherence.
 
4. A marginal structural pooled logistic regression model is fit to the mortality outcome data, as a function of time and treatment (with interaction), using inverse-probability of censoring weights from step 3.
 
5. Treatment-specific marginal probabilities of all-cause mortality are estimated from the fit in step 4, from which the causal risk difference, <math>\Delta_{RD}</math>, is estimated along with a two-sided 90% = 100(1-2alpha)% confidence interval (constructed via the bootstrap).
 
6. Taking the type I error rate, alpha, to be 0.05, non-inferiority is concluded if the upper limit of a two-sided 90% = 100(1-2alpha)% confidence interval for <math>\Delta_{RD}</math> is less than the prespecified margin.

Secondary Outcomes	
Cumulative over 7-years from PET:
 
Number of thyroid cancers
 
Number of thyroid ultrasounds
	
Cumulative incidence rate over 7-years from PET or to the end of the study period

	Number of thyroid biopsies Number of thyroid surgeries	
Exploratory Analysis	Types of thyroid cancer diagnoses	Same

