## 4 STUDY DESIGN

### 4.1 OVERALL DESIGN

We hypothesize that all-cause mortality in patients with an incidental thyroid nodule on PET-CT who did not have thyroid ultrasound (the exposure) within 3 months of the PET-CT is non-inferior within a 5% margin to those who have thyroid ultrasound at 7-years. That is, among patients with an incidental thyroid nodule on PET-CT, mortality is no more than 5% larger (in absolute difference) for those who do not have thyroid ultrasound compared to those who do. We will also report mortality differences at landmark timeframes of 1-year, 3-years, 5-years, and 10-years.

Understanding an expected 30%-50% baseline 10-year mortality rate in patients who undergo PET imaging at our institution, a 5% non-inferiority margin was chosen based on the most conservative proposed margin by 2 thyroid endocrinologists (one did not respond) and a head and neck surgeon (other proposed margins were 7% and 10%). This margin decision was informed by typical margins of 5% to 10% used in non-inferiority trials of medications with outcomes involving mortality and by recent non-inferiority trials of thyroid cancer treatments. The observational nature of this non-inferiority study and absence of prior studies that show effect sizes for the reference make ideal margin point-estimate and fixed-estimate calculations impossible, but our expert panel method is supported as a practical necessity to provide guidance on the fraction of the point estimate of the active comparator that stakeholders are willing to lose at a cost of gaining other advantages (in this case, likely fewer biopsies and surgeries), as in the point-estimate margin calculation method. Given this careful pre-specification of our margin with this panel decision, we will follow published methodology recommendations and consider re-evaluation of the margin based on the secondary benefits seen in the emulated trial or we may conduct the final analysis without reference to a margin. These decisions will be clearly detailed in final manuscripts.

To estimate group differences in mortality, we will conduct a non-inferiority emulated target trial utilizing clone-censor weighting to address potential immortal time bias introduced by the 3-month grace period. We will adjust for all variables labeled as demographic, potential confounder, or mortality risk adjustor in as listed in the Section 7, below.

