#### **Additional Patient Variables**

#### **Explanation**

sex	Demographic: 1 = male; 2 = female; 3 = other/unknown
adi	Demographic: national area deprivation index on scale 0 (low deprivation) to 100 (high deprivation) based on listed home address in 2025
language	Demographic: self-reported language
race	Demographic: self-reported race
ethnicity	Demographic: self-reported ethnicity
smoking	Potential Confounder: 0 = never; 1 = former; 2 = active; No_self-report = not reported; most recently recorded prior to imaging
alcohol	Potential Confounder: 0 = never; 1 = occasional; 2 = heavy; most recently recorded prior to imaging
obesity	Potential Confounder: 1 = diagnosis of obesity (ICD-10 E66, ICD-9 278.00 or 278.01) at time of imaging examination OR OR cacluated BMI >30 at timepoint within 1 year before and closest to imaging examination; 0 = no diagnosis of obesity or BMI >30
metabolic_syndrome	Potential Confounder: 1 = diagnosis of metabolic syndrome (ICD-10 , ICD-9 277.7) at time of imaging examination; 0 = no diagnosis of metabolic syndrome at time of imaging examination
mi	Mortality Risk Adjustor: Myocardial Infarction: ICD-10 I21.9; ICD-9 410; recorded prior to date of imaging examination
chf	Mortality Risk Adjustor: Congestive Heart Failure: ICD-10 I50; ICD-9 428; recorded prior to date of imaging examination
pvd	Mortality Risk Adjustor: Peripheral Vascular Disease: ICD-10 I70, I73; ICD-9 443, 440.2, 440.3, 440.4; recorded prior to date of imaging examination

cva	Mortality Risk Adjustor: Cerebrovascular Accident: ICD-10 I60-I63, G45; ICD-9 430-438; recorded prior to date of imaging examination
dementia	Mortality Risk Adjustor: Dementia: ICD-10 F01-F03; ICD-9 290; recorded prior to date of imaging examination
cpd	Mortality Risk Adjustor: Chronic Pulmonary Disease: ICD-10 J42-J44; ICD-9 491-492; recorded prior to date of imaging examination
ctd	Mortality Risk Adjustor: Connective Tissue Disease: ICD-10 M30-M36; ICD-9 710; recorded prior to date of imaging examination
pu	Mortality Risk Adjustor: Peptic Ulcer Disease: ICD-10 K25-K28; ICD-9 531-534; recorded prior to date of imaging examination
ld	Mortality Risk Adjustor: Liver Disease: ICD-10 K70-K77; ICD-9 570-573; recorded prior to date of imaging examination
dm	Mortality Risk Adjustor: Diabetes Mellitus: ICD-10 E8-E13; ICD-9 249-250; recorded prior to date of imaging examination
hemiplegia	Mortality Risk Adjustor: Hemiplegia: ICD-10 G81; ICD-9 342; recorded prior to date of imaging examination

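### Three of about 52 adjustment covariates do not meet the plan's own baseline rule: Brain carries the lung definition, the deprivation index uses a 2025 address, and radiation has no pre-PET limit

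*Combined protocol and SAP*

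**What the plan says.** Section 1.2, step 3 of the emulation column, fits the adherence model "adjusting for a priori specified baseline factors that predict adherence". Follow-up starts at the PET-CT ("PET-CT date, not equivalent to treatment assignment"), so baseline means that date. Section 4.1 defines the covariate set by label: "We will adjust for all variables labeled as demographic, potential confounder, or mortality risk adjustor", pointing to the Section 7 list. Section 8.4.3 refers back to Section 1.2 and gives no other list.

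Three rows in Section 7 matter here.

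- **Brain** (potential confounder): "PET-CT report indicate that there is likely primary malignancy or metastases in the lungs". The Lung row, two rows below, has the same words. Face lies between them and has its own definition.
- **adi** (demographic): the national area deprivation index "based on listed home address in 2025". Eligibility in Section 5.1 is "Thyroid nodule on PET-CT performed 1/1/2015 to 12/31/2021".
- **radiation_binary**: "Mortality Risk Adjustor: Radiation Therapy: CPT 77401-77416, G6003-G6014, 77385-77386, G6015-G6016". The entry stops there, with no date condition.

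**The concern.** A covariate in the weight model should be fixed at time zero and should measure what its name says. Brain fails the second test. The other two, as written, can fail the first.

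The estimate is a per-protocol effect from non-randomized data, and the weights are its main protection against confounding. If brain involvement is not measured, a strong predictor of death that may also steer clinicians away from a thyroid work-up is left out. If radiation after the PET counts, the model conditions on something that can follow from the work-up or from later progression, and that only patients who live long enough can receive. If the address is read in 2025, survivors' records can still change after the PET while those of patients who have died cannot, so the timing of the measurement depends on the outcome.

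The Brain row also reaches the stratified analyses: Sections 4.1 and 8.4.5 stratify by disease status, which Section 4.1 says includes metastatic sites other than lymph nodes.

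**Working it through.** The plan states no figure on this point, so there is none to reproduce. The check is mostly a side-by-side reading, followed by two illustrations of scale.

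**1. How many covariates are affected.** Counting the Section 7 rows that carry one of the three labels:

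- demographic: 6 (age, sex, adi, language, race, ethnicity)
- potential confounders other than PET-report findings: 7
- mortality risk adjustors: 19
- PET-report disease-status variables, NeckNodes to Muscle: 20

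6 + 7 + 19 + 20 = 52. Three of the 52 are in question.

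**2. Brain.** With Brain = Lung, a design matrix of intercept, Brain and Lung has rank 2, not 3. One coefficient cannot be estimated, but the fitted probabilities, and so the weights, are the same as with Lung alone. The duplicate column does no harm in itself; the harm is the missing variable. Section 7 adds a second uncertainty. It says the last 12 disease-status variables come from the language model, yet 20 rows are defined by the PET report. Counted literally, the last 12 start at Pleura and leave out Brain, so the text does not settle how Brain is extracted.

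**3. adi.** Shortest gap: 31 December 2021 to 1 January 2025, 3.0 years. Longest gap: 1 January 2015 to 31 December 2025, just under 11.0 years. By contrast, smoking and alcohol take the latest record before imaging.

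**4. radiation_binary.** Every other diagnosis or treatment row among the mortality risk adjustors is tied to a time before or at the scan: the comorbidity, cancer and head/neck cancer rows to before imaging, obesity_icd to the time of imaging, and Fiveyr_atPET to cancers diagnosed before the PET. The next row, priorneckradiation, uses the same procedure codes and limits them to before imaging.

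**5. Scale, for illustration only.** All inputs below are assumptions. The risk difference (RD) is no ultrasound minus ultrasound, to be read against the 5-point margin.

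*Omitted brain disease.* Bias is roughly the residual difference in prevalence between strategies, after all other adjustment, times the excess 7-year risk of death.

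| Residual difference | Excess risk 20 points | Excess risk 50 points |
|---|---|---|
| 1 point | 0.01 × 0.20 = 0.2 points | 0.01 × 0.50 = 0.5 points |
| 5 points | 0.05 × 0.20 = 1.0 point | 0.05 × 0.50 = 2.5 points |

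*Post-PET radiation.* This is a simplified point-treatment version of the weighting. Assume that ultrasound has no effect on death and 30% have it; that 40% are frail, unmeasured, with death risk 0.60 against 0.25; and that radiation probability is 0.15, plus 0.30 if frail, plus 0.10 if ultrasound was done.

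- No ultrasound: P(radiation) = 0.6 × 0.15 + 0.4 × 0.45 = 0.27. Frail share: 0.18/0.27 = 0.667 with radiation, 0.22/0.73 = 0.301 without.
- Ultrasound: P(radiation) = 0.6 × 0.25 + 0.4 × 0.55 = 0.37. Frail share: 0.22/0.37 = 0.595 with radiation, 0.18/0.63 = 0.286 without.
- Overall P(radiation) = 0.7 × 0.27 + 0.3 × 0.37 = 0.30.
- Spurious RD = 0.35 × [0.30 × (0.667 − 0.595) + 0.70 × (0.301 − 0.286)] = 0.011, or about 1.1 points.

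If ultrasound does not change later radiation, the same formula gives 0. If frail patients are instead 10 points less likely to have radiation, the frail shares become 0.182 and 0.427 (no ultrasound) and 0.286 and 0.430 (ultrasound), with overall P(radiation) 0.14. The result is 0.35 × [0.14 × (0.182 − 0.286) + 0.86 × (0.427 − 0.430)], about −0.6 points. The sign therefore depends on assumptions that the documents do not settle.

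No comparable figure is offered for adi, because the documents do not say how addresses are updated.

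**The case against.** Five counter-arguments deserve weight.

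- **Brain looks like a typing error.** The variable is named Brain, Lung has its own row, and the version 1.1 change summary says these covariates were revised to match an updated extraction tool. Neither the prompt nor the data are shown, so the extracted field may be correct. This stands, and it means checking before re-running anything.
- **Brain disease is not wholly invisible.** The general cancer flag and Fiveyr_atPET partly reflect a brain cancer diagnosed before the PET. This also stands. What literal coding would lose is a variable specific to brain involvement reported on the scan.
- **radiation_binary is silent rather than contradictory.** Section 1.2 speaks of baseline factors, and the natural reading is that a phrase was left out. That is plausible. But a programmer working from the row would apply no date filter, and the neighbouring row shows that the authors write the limit when they intend it.
- **A 2025 address may equal the baseline address** for patients whose record never changed, and nothing suggests that ultrasound alters neighbourhood deprivation. Both are fair. The index is an imperfect proxy whose error could depend on survival, to an unknown extent. Dropping it outright would exchange that error for no deprivation adjustment at all.
- **The bias figures are assumed.** They are. A 1- to 5-point residual imbalance in brain disease may be too large once the other disease-site variables and Fiveyr_atPET are in the model, and the mix of scan types that would show the brain is not given.

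A reader might infer that the whole weight model fails as a baseline adjustment, or that a bias of a known number of points has been shown. The documents support neither: 49 of the 52 covariates are untouched by this point, and every input to the bias illustrations comes from outside the plan.

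**Conclusion.** The point holds for the wording of three covariate definitions. Brain carries the wrong anatomical site. adi is explicitly dated after every index PET, and its timing depends on survival. radiation_binary lacks the time limit that the comparable rows carry. All three enter an adjustment that Section 1.2 describes as using baseline factors, and nothing elsewhere in the plan corrects them. Followed literally, the rows would change the weights, so this is more than a matter of presentation.

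The effect on the 7-year risk difference cannot be determined from the documents, in size or direction. Under the stated assumptions it runs from nothing to about 2.5 points for the omitted brain variable, and from about −0.6 to 1.1 points for post-PET radiation. Those ranges show that the definitions are worth correcting against a 5-point margin; they do not estimate the bias. Confidence is high on the wording and low on the consequence. The changes should be made before the analysis is run.

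**What to change.** 1. **Brain.** Change the site in the definition from lungs to brain. Check the language-model prompt and the coding script for this field, and re-run it only if the error reached the data. In the same edit, reconcile the stated 12 disease-status variables with the 20 rows listed.
2. **radiation_binary.** Add the pre-imaging restriction already used in the comorbidity rows, and confirm that the extraction query applies it.
3. **adi.** Use the address on file at the PET date, or the nearest one before it, where available. Where it is not, keep the present adi, state the limitation, and add a sensitivity analysis of the primary risk difference without adi.

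The cost is three edits to definitions, a check of the prompt and code, and one re-extraction for addresses, plus a re-run of the Brain field if needed. The main drawback is that some historical addresses may be missing, which is why adi is kept with a sensitivity analysis rather than removed.
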